Study Protocol and Statistical Analysis Plan for NCT 05265624

The Moran AMD Genetic Testing Assessment Study (MAGENTA)

The following pages contain the IRB approved study protocol and statistical analysis plan at the most recent renewal approved on 12/11/2024.

Date: Friday, July 25, 2025 1:00:53 PM

Print

Close

IRB_00150093

Created: 12/15/2021 2:30 PM

PI: [name]

Submitted: 1/31/2022

IRB_00150093

1. Contacts and Title

Title: Magenta: The Moran AMD Genetic Testing Assessment Study

1. Study Introduction

1. Responsible Investigator:

[name]

Email	Training	Col Date
[contact]	7/7/2024 MCG	7/18/2025

a. Position of the Investigator:

Faculty or Non-Academic Equivalent

Student

Staff

Resident/Fellow

Other

2. Contact Persons for the Responsible Investigator:

Name	Email	Training
[name]	[contact]	1/30/2023 MCG
[name]	[contact]	1/31/2023 MCG
[name]	[contact]	8/2/2024 MCG
[name]	[contact]	10/25/2022 MCG
[name]	[contact]	1/4/2023 MCG
[name]	[contact]	6/5/2025 MCG

3. Guests of the Responsible Investigator:

Last Name	First Name	E-Mail
-----------	------------	--------

There are no items to display

4. What type of application is being submitted?

New Study Application (or Amendment/Continuing Review)

5. Title Of Study:

Magenta: The Moran AMD Genetic Testing Assessment Study

6. Study Purposes and Objectives:

This is a follow up study to our Pilot Study IRB # 60413 - Value of genetic counseling and testing for patients who would like to know more about their personal risk of AMD.

Primary Outcome: Change over 1 year in skin carotenoid status in response to genetic risk disclosure

We hypothesize that disclosure of high AMD risk will motivate subjects to make lifestyle changes that will improve the carotenoid levels in the subjects' skin as assessed by Raman spectroscopy and reflectance relative to lower risk disclosure (primary) or deferred disclosure (secondary). We will also compare disclosure of any AMD risk versus deferred disclosure.

Secondary Outcome: Change over 1 year in ocular and serum carotenoid status in response to genetic risk disclosure

We hypothesize that disclosure of high AMD risk will motivate subjects to make lifestyle changes that will improve the carotenoid levels in the subjects' macula and serum as assessed by autofluorescence intensity and lifetime imaging (macula) and HPLC (serum) relative to lower risk disclosure or deferred disclosure.

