9. Provide a summary of the statistical methods, data analysis, or data interpretation planned for this study. Factors for determining the proposed sample size (e.g., power) should be stated.

Feasibility Aim: We will monitor the proportion of people who complete the monitoring and closeout visits by trial arm assignment and provide estimates and 95% confidence intervals for those rates.

Analytic Aim: Our primary analysis will compare follow-up carotenoid level between the randomized early and late disclosure groups while accounting for AMD risk (categorized as high, medium or low) and baseline carotenoid level under the longitudinal model:

Sample Size and Power: Our power calculation for the primary and secondary comparisons utilizes the pilot study data. We found that with 60 patients (after 25% drop-out from 80 enrolled patients) and an allocation ratio of 3:1 to early and late disclosure groups, there is 80% power to detect a 40.5% difference for our primary comparison. This compares favorably with the >100% changes achievable with diet alone.

Specific Aim 2: AMD risk alleles will be individually tested for associations with skin carotenoid status and MPOV using simple linear regression. We will use this step as a variable selection for a multivariable regression. Alleles with p-values less than 0.05 in the univariable analyses will be included in the final multivariable regression, which will additionally control for baseline measures of ocular and systemic carotenoid status.

Effect of Gender as a Biological Variable: Since men and women are anticipated to be enrolled in a 50:50 ratio, gender as a biologic variable will be assessed in all analyses.

Missing data: To assess risk of bias due to missing data, patterns of missing measurements across follow-up visits will be displayed for the primary and secondary outcomes. Reasons for missing measurements will be tabulated with a focus on differentiating missed measurements for logistical reasons from dropout or intermittent missingness potentially related to the condition of the patient.

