Because we are using restricted maximum likelihood estimation, our statistical inferences for the primary and the numeric secondary outcomes will remain valid if missing data follows a missing at random (MAR) pattern (Little & Rubin, 2014). Nonetheless, if more than 10% of subjects have missing outcome measurements for any of the follow-up visits, i.e. we have less than 80 complete patients, or if comparisons of baseline characteristics between patients with missing and non-missing measurements indicate significant imbalances, we will apply multiple imputation (MI) to further address missing outcome scores (Rubin, 2004). MI incorporates baseline and follow-up factors beyond the variable being analyzed into imputation models to account for dependence of missing data on other factors. We will use the fully sequential imputation method to generate imputed values (Van Buuren, 2007).

Title: Magenta: The Moran AMD Genetic Testing Assessment Study

Consent Process

1. The following investigators and internal staff will obtain consent (as indicated on the Study Location and Sponsors Page):

[name] University of Utah

[name] University of Utah

List by name, role, and affiliation any others who will obtain consent (e.g. [name], Co-Investigator, etc.).

2. Describe the location(s) where consent will be obtained.

At the Moran Eye Center

3. Describe the consent process(es), including the timing of consent. Describe whether there is a waiting period between the consent process and obtaining consent from the participant (i.e., any time between informing participants and actually obtaining consent).

Participants who meet pre-screening criteria will be invited to schedule a baseline visit where written informed consent will be obtained. There will be adequate time between pre-screening and baseline for the participant to review the consent.

4. Describe what measures will be taken to minimize the possibility of coercion or undue influence.

It will be explained to participants that they may not benefit directly from participating and that they can still receive the same standard of care should they decide not to participate.

5. Describe the provisions that are made to allow adequate time to exchange information and questions between the investigator and participant.

The investigators will allow as much time as needed when obtaining consent and will encourage the participants to ask questions before they decide whether or not to participate.

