3. Describe the types of reports that will be produced by the monitoring entity (e.g., safety, study progress, interim analysis, etc.):

DSMB reports

4. Describe the specific triggers or stopping rules for the study:

a. Under what conditions will a participant be withdrawn from the study?

- Patient withdrawal of consent at any time.
- Investigator determines it is in the best interest of the patient.
- Patient non-compliance with study visits or testing.

b. Under what conditions will the study be modified or stopped?

If any concerning safety signals are discerned

5. How often will the data and events be reviewed by the monitoring entity (e.g., after every 5 submits, monthly, quarterly, twice a year, etc.):

Every 6 months

Title: Magenta: The Moran AMD Genetic Testing Assessment Study

6. Risks and Benefits

1. Describe the reasonable foreseeable risks or discomforts to the participants:

There is a risk of loss of confidentiality from medical record review, but procedures are in place to prevent any such loss.

There will be brief discomfort from the needle stick. It is possible that there will be bruising or oozing of blood afterwards. Rarely, there is a risk of infection.

There are no expected side effects from the light exposure for the skin measurement. It is important not to look at the laser directly for a long period of time.

Participants eyes will be dilated for ophthalmic imaging and macular pigment measurements. Dilation causes mild blurry vision and light sensitivity for several hours. Rarely there can be an allergic reaction to or closed angle glaucoma from the dilating drops, or a corneal scratch from rubbing the eyes. High blood pressure, irregular heartbeat or glaucoma may worsen when dilating drops are used. This can be managed and participants are counseled to discuss this with the study coordinator. Participants are advised to wear sunglasses after their visit to help with comfort.

Light levels projected on the retina in this study for macular pigment measurements and ophthalmic photos are well within established safety limits. Participants may notice a central dark spot in their vision similar to the afterimage generated by a camera flash. This afterimage will fade away within approximately 5 minutes.

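### Withdrawal for undefined non-compliance with visits or testing can cause avoidable, possibly informative loss of Month 12 skin carotenoid data, and no planned analysis checks for this

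*Combined protocol and SAP*

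**What the plan says.** The Safety Monitoring Plan, item 4a, gives three conditions for withdrawing a participant: withdrawal of consent, the investigator's judgement of the participant's best interest, and "Patient non-compliance with study visits or testing". The third has no threshold. Nothing says whether skin readings are still sought afterwards or how data collected before withdrawal are used.

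Study Introduction, item 6, defines the primary endpoint: "Primary Outcome: Change over 1 year in skin carotenoid status in response to genetic risk disclosure". The pathway is stated in the same place: "We hypothesize that disclosure of high AMD risk will motivate subjects to make lifestyle changes".

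Study Information, item 9, plans a longitudinal model fitted by REML and states that inferences "will remain valid if missing data follows a missing at random (MAR) pattern". Multiple imputation follows "if more than 10% of subjects have missing outcome measurements for any of the follow-up visits, i.e. we have less than 80 complete patients". A significant difference in baseline characteristics between participants with and without missing data also triggers it. On what imputation adds, the plan says: "MI incorporates baseline and follow-up factors beyond the variable being analyzed into imputation models to account for dependence of missing data on other factors". The same item plans displays of missing-data patterns, a tabulation of reasons, and completion rates by arm with 95% confidence intervals. Power is computed for 60 participants, "after 25% drop-out from 80 enrolled patients".

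**The concern.** A longitudinal REML model can use partial follow-up. A withdrawal rule based on attendance works against it, because it can end collection of data that could still be obtained. The word testing widens the rule. The schedule in Study Information, item 6, includes blood draws and dilated imaging that serve secondary outcomes. A participant who declines one of these could, on the wording, lose all later readings of the primary outcome, a palm scan of about 30 seconds.

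The lost data may not be missing at random. Attendance may reflect the same motivation that is supposed to carry the effect of disclosure to carotenoid levels. Participants know their assignment: the early group has results at Month 1 and the deferred group at Month 12. Loss, or its dependence on motivation, could therefore differ by arm. At stake are the early versus late contrast, the power of a small trial with about 20 people in the deferred arm, and the feasibility aim, since completion by arm would partly measure use of the rule.

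**Working it through.** **1. The plan's drop-out figure.** 80 × (1 − 0.25) = 60, which is 45 v 15 at 3:1. This reproduces. The 40.5% difference at 80% power cannot be checked, because SD, alpha and sidedness are not given. Assuming two-sided 5% and a normal approximation, the detectable difference is (1.960 + 0.842) × √(1/45 + 1/15) = 0.835 SD, so the implied SD is 40.5/0.835 = 48.5%. A t-test gives 0.849 SD; a one-sided test gives 0.741 SD.

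**2. What loss costs in power.** At that SD and a 40.5% difference, power is 90% with all 80 analysed, 80% with 60, 74% with 52, 71% with 48 and 63% with 40. How many of the planned 20 losses come from item 4a is not stated.

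**3. How the rule could multiply missed visits.** Four visits follow disclosure (Months 3, 6, 9 and 12). Suppose each is missed independently with probability p. Month 12 is then missing with probability p if people stay in, and 1 − (1 − p)⁴ if the first miss ends follow-up. With p = 0.052 (an assumption), that is 5.2% against 1 − 0.948⁴ = 19.2%. The missed visit itself is missing either way; the rule adds only the later ones.

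**4. Whether the contrast is biased.** This was simulated with 60,000 participants per scenario at 3:1. Latent motivation M is standard normal. The outcome is a baseline term (SD 0.7), plus 0.7·M rising linearly from Month 1 to Month 12, plus noise (SD 0.35). The log-odds of missing a visit is −2.9 − b·M. Month 12 means were estimated by maximum likelihood under MAR using all visits. The rule was taken as withdrawal at the first missed visit. That threshold, b and the outcome model are assumptions. Bias is estimated minus true early − deferred difference, in Month 12 SDs.

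| Scenario | Month 12 missing, deferred/early: no rule | with rule | Bias: no rule | with rule |
|---|---|---|---|---|
| b = 1 in both arms, no effect | 7.5/7.5% | 24.2/24.4% | −0.002 | −0.004 |
| b = 1 in deferred only, no effect | 7.4/5.2% | 25.4/19.1% | −0.016 | −0.113 |
| b = 1 in early only, no effect | 5.3/7.6% | 19.0/24.7% | +0.019 | +0.112 |
| b = 1 in both, disclosure raises M by 0.5 | 8.0/4.8% | 24.5/16.7% | −0.008 | −0.032 |
| b = 1.5 in both, disclosure raises M by 0.8 | 10.5/4.1% | 28.1/13.1% | −0.028 | −0.091 |

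In the first row each arm mean is biased upward by about 0.11 SD with the rule (0.02 without), but the biases cancel in the contrast. In the last two rows a true difference is attenuated: 0.332 to 0.300 SD, and 0.525 to 0.434 SD.

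**5. Whether the planned analysis would reveal this.** The planned 25% drop-out exceeds the 10% trigger, so imputation should be expected. It conditions on observed factors, as REML conditions on observed outcomes. Both rest on MAR, and no analysis in item 9 departs from it.

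**The case against.** The strongest reply is that the rule has been read too literally. Item 9 expects intermittent gaps and separates them, and logistical absences, from drop-out. If one missed visit always ended participation, intermittent gaps could not arise. Participants are also paid for each visit completed. This stands: withdrawal at a single missed visit is not established, and the simulation's rule is an extreme version of the text.

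A reader might go further and infer that the rule removes the least motivated people and so biases the trial. The documents do not support this. They do not link absence to low motivation; the outcome is a skin measurement, with motivation only the hypothesised pathway; and nothing says that data collected before withdrawal are discarded. The direction is open too. Deferred participants have no result to act on, which may weaken attendance, but they receive it only at Month 12, which is a reason to stay.

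A reader might also attach a figure. Assume a log-scale SD of 0.40, the least motivated 20% lost from the early arm and 40% from the deferred arm, and a correlation of 0.3 to 0.5 between motivation and outcome. Mean motivation among those retained is then 0.350 and 0.644, and the bias is −0.294 × 0.40 × (0.3 to 0.5) = −0.035 to −0.059 log units. Relative to ln 1.405 = 0.340, that is 10% to 17% of the detectable effect. The arithmetic is sound but does not measure the rule. It attributes all drop-out to motivation, has no comparison without the rule, ignores data collected before withdrawal, and changes sign if the heavier loss is in the early arm. Type I error figures from such a scenario, or a fall in the detectable difference from 40.5% to about 36% on the supposition that loss drops to 10%, are illustrative for the same reasons.

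The tabulations, baseline comparison and imputation are real safeguards and would help describe the loss. They do not recover readings that were never sought, and they do not test the MAR assumption.

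**Conclusion.** The point holds as an avoidable weakness, not as a demonstrated bias. The plan contains an open-ended ground for study withdrawal that can discard obtainable primary-outcome data. It makes no provision for continued collection and plans no check for data missing not at random. The effect cannot be sized from the documents, which give no SD, no share of drop-out due to this rule and no loss by arm. Under the assumptions above, the rule's effect on the arm contrast ranges from about zero (equal dependence, no true effect) to about 0.11 SD in either direction (dependence in one arm only), with attenuation of a true effect if disclosure itself raises motivation. The loss of power and the mixing of the rule into completion rates do not need informative loss; they need only that the rule is used. The change is worth making because it is cheap.

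**What to change.** In the Safety Monitoring Plan, item 4a, remove non-compliance with visits or testing as a reason for study withdrawal. Leave consent withdrawal and the investigator's best-interest judgement as they are. State that participants who miss visits or tests remain in the study, are analysed as randomised, and are invited to every remaining visit, above all Month 12.

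In Study Information, item 9, add one sensitivity analysis for outcomes still missing: impute under MAR, shift the imputed values by a delta set separately for each arm, and report the range of deltas over which the conclusion holds.

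The cost is a short protocol change, some extra scheduling for participants who attend irregularly, and one additional analysis.

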[name]

Submitted: 1/31/2022

Title: Magenta: The Moran AMD Genetic Testing Assessment Study

Investigational Use of a Device

1. What is the initial risk determination of the device study according to the investigator and/or sponsor?

The study is a non-significant risk (NSR) device study.

a. Provide IDE (or HDE) Number(s) for significant risk devices:

IDE/HDE #	Device Name	IDE/HDE Holder
-----------	-------------	----------------

There are no items to display

b. Attach verification of the IDE (or HDE) number for significant risk devices to the Documents and Attachments page. Please check the method by which you choose to verify the IDE (or HDE) number:

There are no items to display

2. Describe the plan to control, store, and dispense the investigational device or humanitarian use device. This plan should ensure that the device is only used by qualified investigator(s) for the participants enrolled in this research project.

There are four investigational devices being used in this study. The first is the Heidelberg MOPD module software program, the second is the Heidelberg FLIO system and the third is the Heidelberg High-Resolution OCT system. [name] personally oversees the use of the Heidelberg systems. He does not allow use of these devices for routine medical care.

The third investigational device to be used in this study is the RSS skin scanner. [name] previously held a patent for the scanner and controls access to the scanner and trains study staff in its use. He does not allow use of the skin scanner for routine medical care, nor would it be relevant to standard care.

PI: [name]

Submitted: 1/31/2022

Title: Magenta: The Moran AMD Genetic Testing Assessment Study

Non-Significant Risk Device

Review the following definition of a non-significant risk (NSR) device:

1. The medical device is not a significant risk device, because all of the following are true:
 - a. The medical device is NOT intended as an implant that presents a potential for serious risk to the health, safety, or welfare of a subject.
 - b. The medical device is NOT purported or represented to be for a use in supporting or sustaining human life that presents a potential for serious risk to the health, safety, or welfare of a subject.
 - c. The medical device is NOT for a use of substantial importance in diagnosing, curing, mitigating, or treating disease, or otherwise preventing impairment of human health that presents a potential for serious risk to the health, safety, or welfare of a subject.
 - d. The medical device is does NOT otherwise present a potential for serious risk to the health, safety, or welfare of a subject.
2. The medical device is not banned.

1. Provide justification of why the investigational medical device used in this study meets the definition of a NSR device.

In this study, we are using the Heidelberg MultiColor Spectralis instrument to measure and image macular pigment optical density (MPOD). This commercial device is FDA cleared for use in eye clinics throughout the United States to image the retina in various ways. Heidelberg has provided us with a beta version of a software package which analyzes autofluorescence images to measure MPOD. Since this software has not yet been submitted to the FDA for approval, we can use it only under an IRB approved protocol. This software analyzes collected images in a new way, but the actual collection of the images is done in the usual manner for the instrument, so there are no significant risks of harm to the subjects.

Fluorescence Lifetime Imaging Ophthalmoscopy (FLIO), developed by Heidelberg Engineering, is a new imaging technique that may provide more information than current fundus autofluorescence imaging. FLIO allows "reproducible measurements of fluorescence lifetimes of the macula in healthy subjects" (Dysli, C. et al) FLIO is a non-significant risk device exempt from IDE approval. It is not approved for any diagnostic or therapeutic decision and must be used under IRB approval and agreement from Heidelberg.

The Heidelberg high-resolution OCT (HR-OCT) uses a diode light source that more than doubles the axial resolution of the images, allowing unprecedented imaging of the layers of the retina. The Heidelberg Engineering SPECTRALIS HighRes OCT is considered to be a Non-Significant Risk (NSR) device for the following reasons: (1) The technical safety of the device corresponds to the international state of the art for medical devices. It is a variant of the SPECTRALIS, an ophthalmic diagnostic medical device that has been marketed in the USA, the EU and other regions and countries since 2007. During this time there have been no recalls or serious incidents with the SPECTRALIS due to technical hazards. (2) The SPECTRALIS HighRes OCT does not otherwise affect the risk to the user or the study subject: a. Information of the investigational SPECTRALIS HighRes OCT device will not be used to drive clinical decisions in the study. (3) The SPECTRALIS HighRes OCT is non-contact medical device. SPECTRALIS HighRes OCT is not an implant. The SPECTRALIS HighRes OCT does not support or sustain human life. The SPECTRALIS HighRes OCT is a non-contact ophthalmic imaging and analyzing device that supports the user in diagnosing. It uses existing technology and specialized software and does not present an increased risk to health, safety, or welfare of a subject. There is no other potential for serious risk.

The resonance Raman skin scanner measures carotenoids in the skin by shining a blue light on the palm of the hand for about 30 seconds. It is a higher sensitivity research version of the commercially available BioPhotonic scanner made by

NuSkin/Pharmanex. The laser power is less than many laser pointers and is completely safe for prolonged skin exposure, so it poses no significant risk to the subjects.

Title: Magenta: The Moran AMD Genetic Testing Assessment Study

Genetic Research

1. Describe the risks to participants in regard to genetic testing, including applicable risks to privacy and confidentiality, as well as psychological and social risks.

There is a risk of loss of confidentiality from medical record review, but procedures are in place to prevent any such loss.

There will be brief discomfort from the needle stick. It is possible that there will be bruising or oozing of blood afterwards. Rarely, there is a risk of infection.

There are no expected side effects from the light exposure for the skin measurement. It is important not to look at the laser directly for a long period of time.

Participants eyes will be dilated for ophthalmic imaging and macular pigment measurements. Dilation causes mild blurry vision and light sensitivity for several hours. Rarely there can be an allergic reaction to or closed angle glaucoma from the dilating drops, or a corneal scratch from rubbing the eyes. High blood pressure, irregular heartbeat or glaucoma may worsen when dilating drops are used. This can be managed and participants are counseled to discuss this with the study coordinator. Participants are advised to wear sunglasses after their visit to help with comfort.

Light levels projected on the retina in this study for macular pigment measurements and ophthalmic photos are well within established safety limits. Participants may notice a central dark spot in their vision similar to the afterimage generated by a camera flash. This afterimage will fade away within approximately 5 minutes.

Some subjects may experience anxiety or distress upon learning their genetic risk of AMD or their assignment to the deferred disclosure group. A trained genetic counselor is available to address any subject questions or concerns about their genetic testing results. If subjects experience significant distress or anxiety, they will be referred to [name] for psychological counseling at no cost to the participant.

2. Describe the privacy protections in place for participants in regard to genetic testing. This includes how family member privacy will be protected.

We will not discuss genetic results with anyone other than the participant to whom they belong or authorized members of the study team.

3. Are you performing whole genome or whole exome sequencing?

Yes No

4. Describe the confidentiality protections in place for participants' genetic information. Discuss if and how data will be shared and protected outside the local study team.

The Genetic testing in this study is done by a research lab that is not CLIA certified. Results from the research lab will be kept in the research record and be disclosed to participants, but will not be included in the electronic medical record.

Genetic testing for AMD risk is not available through a CLIA-certified lab so we will be unable to refer participants for confirmatory testing.

The research lab will not identify incidental genetic findings.

5. Will incidental findings relevant to individuals or families be communicated to the participants?

Yes No

If yes, answer the questions below:

a. Describe the process for determining which incidental findings will be returned to the participants.
Describe the information and expert consultation that will be used to make this determination.

b. Indicate the process that will be used to return information about incidental finding to participants:

There are no items to display

If Other, describe and justify the process that will be used:

6. **Will genetic information or samples be submitted to a national or international database because of this research?**

- Yes
- No

PI: [name]

Submitted: 1/31/2022

Title: Magenta: The Moran AMD Genetic Testing Assessment Study

8. Resources and Responsibilities

1. * State and justify the qualifications of the study staff:

The PI and physician sub-investigators have a medical license to allow them to make medical decisions and provide patient care. They are qualified by certification and experience to conduct the study.

Study Coordinators have experience in conducting clinical studies and receive protocol specific training from the investigator and other study team members.

Ophthalmic imagers are qualified by experience and/or certification to conduct protocol specified procedures.

The genetic counselor is licensed in the state of Utah and experienced in clinical research.

A graduate student from the Nutrition department with a background in optometry will perform the serum carotenoid analyses and the Spectralis AFI and FLIO imaging and will participate in data analysis and manuscript preparation.

2. * Describe the training that study staff and investigators will receive in order to be informed about the protocol and understand their research-related duties and functions:

Study specific training includes study-specific or staff meetings, e-mail correspondence, and teleconferences. All study staff members and investigators agree to conduct the study according to good clinical practices and the ethical conduct of research. Training documentation, including but not limited to study meetings, GCP certificates and CITI certificates will be maintained in the study file.

3. * Describe the facilities where the research activities will be performed (e.g. hospitals, clinics, laboratories, classrooms/schools, offices, tissue banks, etc.).

Research visits and data analysis will be conducted at the Moran Eye Center.

Genetic analysis will be conducted at the Moran Eye Center in the [name] Lab. Serum carotenoid analysis will be conducted at the Moran Eye Center in the [name] Lab.

4. * Describe the medical or psychological resources available at this site (and other participating sites, if applicable) that participants might require as a consequence of the research. If not applicable, please state.

[name], LCSW, Associate Professor of Ophthalmology and Visual Sciences at the University of Utah, is Director of the Moran Eye Center's Patient Support Program. She will counsel any subjects who experience anxiety or distress from learning of their genetic risk of AMD or from their assignment to deferred disclosure.

PI: [name]

Submitted: 1/31/2022

Title: Magenta: The Moran AMD Genetic Testing Assessment Study

Documents and Attachments

If any of your documents (such as investigational brochures, sponsor protocols, advertisements, etc.) are not available in an electronic format, please scan and save them as PDF files or contact our office for assistance.

Naming Documents: Please use the title field to clearly indicate the content of each form. The name you enter will be listed on your approval letter. Use names that will differentiate from earlier versions.

Examples:

Consent Document Control Group 04/14/05

Consent Document Treatment Group 4/14/05

Sponsor Protocol 04/14/05 Version 2

Assent Document(Highlighted Changes)

[Apple/Macintosh Users: MS Word documents must have a .doc file extension. See ERICA home page for instructions.](#)

[Print View: IRB Draft Protocol Summary](#)

eProtocol Summary:

Name	Version	Date Created	Date Modified	Date Approved
------	---------	--------------	---------------	---------------

There are no items to display

Consent Documents, Consent Cover Letters, Consent Information Sheets, Consent Scripts, etc.:

Name	Version	Date Created	Date Modified	Date Approved
------	---------	--------------	---------------	---------------

There are no items to display

Parental Permission Documents:

Name	Version	Date Created	Date Modified	Date Approved
------	---------	--------------	---------------	---------------

There are no items to display

Assent Documents:

Name	Version	Date Created	Date Modified	Date Approved
------	---------	--------------	---------------	---------------

There are no items to display

VA Consent Documents:

Name	Version	Date Created	Date Modified	Date Approved
------	---------	--------------	---------------	---------------

There are no items to display

Surveys, Questionnaires, Interview Scripts, etc.:

Name	Version	Date Created	Date Modified	Date Approved
------	---------	--------------	---------------	---------------

There are no items to display

Full Protocol (company protocol, sponsor protocol, investigator-initiated protocol, etc.):

Name	Version	Date Created	Date Modified	Date Approved
------	---------	--------------	---------------	---------------

There are no items to display

Investigational Brochure (IB) for Investigational Drug or Drug/Device Package Insert:

Name	Version	Date Created	Date Modified	Date Approved
------	---------	--------------	---------------	---------------

There are no items to display

Grant Application:

The Federal Government is a direct or indirect sponsor of your research. You are required to provide a copy of the grant proposal, grant award, or sub-award.

By submitting to the IRB, you are confirming the grant and the study protocol are consistent (Design, Study Population, Study Objectives and Goals, Test Interventions and Procedures, etc.)

Name	Version	Date Created	Date Modified	Date Approved
There are no items to display				

Literature Cited/References:

Name	Version	Date Created	Date Modified	Date Approved
There are no items to display				

Principal Investigator's Scholarly Record (CV/Resume):

Name	Version	Date Created	Date Modified	Date Approved
 [name] CV 13 May 2015.pdf(0.01)	0.01	5/14/2015 1:10 PM	5/14/2015 1:10 PM	
 [name] CV 13 Sep 2017.pdf(0.01)	0.01	1/9/2018 3:49 PM	1/9/2018 3:49 PM	
 [name] CV exp 9.13.2021.pdf(0.01)	0.01	4/19/2021 12:42 PM	4/19/2021 12:42 PM	

Faculty Sponsor's Scholarly Record (CV/Resume):

Name	Version	Date Created	Date Modified	Date Approved
There are no items to display				

Other Stamped Documents:

Name	Version	Date Created	Date Modified	Date Approved
There are no items to display				

Recruitment Materials, Advertisements, etc.:

Name	Version	Date Created	Date Modified	Date Approved
There are no items to display				

Other Documents:

Name	Version	Date Created	Date Modified	Date Approved
There are no items to display				

IRB_00150093

Created: 12/15/2021 2:30 PM

PI: [name]

Submitted: 1/31/2022

IRB_00150093

Biosafety Registration

Title: Magenta: The Moran AMD Genetic Testing Assessment Study

Biosafety Registration

Biosafety Office Registration

Are you manipulating unfixed human samples (blood, tissues, organs, cells, etc.) in a University of Utah research laboratory (for storage or work in a diagnostic lab select “No”):

Yes: already registered and approved by the Biosafety Office.

Biosafety Office Registration Number

BOR_00000356

Institutional Biosafety Committee Registration

Are you introducing recombinant or synthetic nucleic acids (such as viral vectors, plasmids, or oligonucleotides, or cells containing recombinant or synthetic nucleic acids) or human pathogens (e.g., Viruses, Bacteria, Fungi or Parasites) into Research Subjects:

No

Title: Magenta: The Moran AMD Genetic Testing Assessment Study

Finish Instructions

Finish Instructions

1. To view errors, select the "Validate" option at the top-left of the page. If you have errors on your application, you won't be able to submit it to the IRB.
2. Selecting the Finish button will NOT submit the application to the IRB. You MUST select the "Submit" option on the workspace once you've selected the "Finish" button.
3. If your study has a faculty sponsor: Once the PI submits the application, it will be sent to the faculty sponsor for final approval. The IRB cannot review the study until the faculty sponsor submits the application to the IRB.
